## 10.1.1 Sensitivity Analyses for PFS

#### 10.1.1.1 Stratification factors

A sensitivity analysis of invPFS may be performed using the actual supportive data from FMI CTA and EDC to derive the randomization strata groups:

- HRD status based on FMI CTA
- Disease status (no residual disease vs residual disease) based on EDC data; and
- Timing of surgery (primary surgery vs. interval debulking) based on EDC data.

A summary table, broken out by treatment group and overall, with the number of patients that have data that is different between the randomization stratification factors compared to the collected data will also be provided together with a patient listing with details.

#### 10.1.1.2 Censoring Distribution

Sensitivity analyses for invPFS will be performed to evaluate the impact of censored patients.

The following sensitivity analyses will be performed:

- All scans and data: According to the study protocol, tumor scans were to continue to be performed during follow up for patients who discontinued without a documented disease progression event by RECIST v1.1. As such, a sensitivity analysis will be performed in which all tumor scans or death events will be included for assessment of PFS even if the patient discontinued study treatment or initiated a subsequent anticancer therapy. This is in accordance with the EMA guidelines.
- Clinical progression or withdrawal: To evaluate further impact on early treatment discontinuations, a sensitivity analysis will be performed in which patients who discontinued oral study drug due to clinical progression or who withdrew consent from treatment will also be considered events of invPFS on the date of the last dose of study drug.

Additional sensitivity analyses may also be performed to evaluate the robustness of the study results. These analyses will be considered exploratory and will likely be motivated by the observed results.

Confidential 31 of 52

## **10.2** Secondary Efficacy

## 10.2.1 PFS by Blinded Independent Radiology Review (bicrPFS)

Note: Blinded independent radiology review (BICR) of scan data is on hold and analysis of this data will only be performed if the primary endpoint of investigator PFS is statistically significant.

The secondary endpoint of bicrPFS by RECIST v1.1 is defined as the time from randomization to disease progression, according to RECIST v1.1 criteria as assessed by BICR, or death due to any cause, whichever occurs first. The time to bicrPFS will be calculated in months as the time from randomization to disease progression +1 day. Only scans or deaths prior to and on the start of any subsequent anticancer treatment will be used in PFS analysis. Any death or progression occurring within two missing expected scan assessments will be included in the analysis. Two missed scans or visits is defined as a duration of 26 weeks  $(12 \times 2 + 2)$  for the first 3 years and 50 weeks  $(24 \times 2 + 2)$  thereafter. Events occurring immediately after 2 consecutive missed scans will be censored as below.

Censoring rule: Any patients who do not experience an event of either disease progression or death will be censored on the last on-study tumor assessment prior to start of any subsequent anticancer treatment. Any patients with an event of either disease progression or death following two or more missed expected consecutive scans will be censored on the date of the last on-study tumor assessment prior to gap in scan collection. If a patient does not have any on-study tumor assessments, then the patient will be censored on the date of randomization (ie, Day 1).

The overall tumor assessment date is defined as the latest scan for each visit where multiple scans were utilized to make the overall assessment.

The bicrPFS will be analyzed using the stratified Cox proportional hazard methodology, presenting the estimated hazard ratio with 95% confidence interval between the randomized treatment groups. In addition, a stratified log-rank test of bicrPFS between the randomized treatment groups together with a graphical presentation of unstratified bicrPFS distributions, median bicrPFS with 95% CI, and event rates will be presented as supportive statistics.

BicrPFS is a stand-alone secondary endpoint and will be summarized for the ITT population. In addition, bicrPFS may be summarized by the subgroups of patients by PD-L1 status and HRD classification (tBRCA, non-tBRCA LOHhigh, non-tBRCA LOHlow, and non-tBRCA LOHunknown and HRD [tBRCA + non-tBRCA LOHhigh]) as needed.

#### 10.2.2 Overall Survival

The overall survival is defined as the time from randomization to death by any cause. Overall survival will be calculated in months as the time from randomization to death +1 day. Patients who have not died will be censored on the date the patient was last known to be alive.

Confidential 32 of 52

The overall survival will be analyzed using the stratified Cox proportional hazard methodology and a stratified log-rank test (considered the official test for the hierarchical testing). The stratified hazard ratio from the Cox proportional hazards model will be used to estimate the HR between the randomized treatment groups.

It is anticipated that the data for overall survival may be somewhat immature at the time of the primary endpoint analysis. In order to adjust for multiple analyses of overall survival at a later stage, a stopping rule will be applied. The Haybittle-Peto stopping rule will be applied where any interim (early) overall survival with a p-value<0.001 can be used to claim superiority. This means that a p-value very close to 0.0125 one-sided (two-sided alpha=0.025) can still be utilized at the final analysis which is projected to be once 70% (n~560) of the death events has been collected.

## 10.2.3 Objective Response Rate by RECIST v1.1. as assessed by investigator

The ORR as assessed by the investigator will be analyzed in the subgroup of patients who have measurable target lesions at baseline as assessed by investigator. The confirmed response rate by RECIST v1.1 will be summarized. The confirmed response rate is defined as the proportion of patients with a confirmed CR or PR (confirmed = subsequent tumor assessment at least 28 days after first response documentation with PR or CR). The ORR will be summarized with frequencies and proportions together with 95% CI and compared between treatments by using a stratified Cochran-Mantel-Haenszel (CMH) test which will be the official test used for the hierarchical testing outlined in Section 3.4. In addition, the frequency and proportion of patients will be summarized based on the below best confirmed response categories:

- CR:
- PR;
- SD;
- PD: and
- Not evaluable

## 10.2.4 Duration of Response by RECIST v1.1. as assessed by investigator

The Duration of Response (DOR) as assessed by investigator will be analyzed in the subgroup of patients who have a confirmed response by RECIST v1.1. DOR for any confirmed RECIST CR or PR will be measured from the date of the first response until the first date that progressive disease is documented. DOR will be calculated in months as the time from the first date of the scan showing a response to the first scan with disease progression +1 day. Any patients with an ongoing response will be censored at the date of the last post-baseline scan.

The DOR will be analyzed using Cox proportional hazard methodology and a log-rank test. In addition, a graphical presentation of DOR distributions, median DOR with 95% CI, and event rates will be presented.

Confidential 33 of 52

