it being supportive of the primary endpoint. BicrPFS is defined as the time from randomization to disease progression, according to RECIST v1.1 criteria as assessed by BICR, or death due to any cause, whichever occurs first. Only tumor scans prior to start of any subsequent anticancer treatment are included.

OS is defined as the time from randomization to death due to any cause.

Analyses of ORR will be performed in the subgroup of patients with measurable disease at baseline and will be summarized with frequencies and percentages. DOR will be tested as a stand-alone secondary endpoint, outside of the step-down procedure for multiplicity adjustment. DOR is defined as the interval from the first documentation of objective response (RECIST v1.1) to the earlier of the first documentation of disease progression (per RECIST v1.1) or death from any cause.

Safety Analyses

All safety analyses will be presented by randomized treatment group for all patients in the safety population (ie, all treated patients). Any patients enrolled in the open-label safety cohorts will be included in this safety analysis population.

Adverse events, clinical laboratory results, vital signs, ECOG performance status, body weight, and concomitant medications/procedures will be tabulated and summarized. Adverse events will be summarized overall and separately for serious adverse events (SAEs), AEs leading to discontinuation/treatment interruptions/dose reductions, AEs leading to death, and NCI CTCAE v5.0 Grade 3 or higher AEs. Body weight and vital signs will be summarized descriptively (N, mean, standard deviation, median, minimum, and maximum).

Independent Data Monitoring Committee

An IDMC will be established to review safety and efficacy data in compliance with a prospective charter. The IDMC will be comprised of oncologists with experience in treating women with ovarian cancer and a statistician, all of whom are not otherwise involved in the study as investigators.

The IDMC will:

- Review safety and efficacy of rucaparib and nivolumab compared with placebo, as well as the rucaparib + nivolumab combination compared to monotherapy to ensure the study is beneficial to patients.
- Ensure the study is conducted in a high-quality manner.
- Monitor the size of the tBRCA subgroup.

Results from the open-label safety cohort(s) will be shared with the IDMC.

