9.6.2.4 Duration of Response

The duration of response (DOR) as assessed by investigator will be analyzed in the subgroup of patients who have a confirmed response by RECIST v1.1. Duration of response is defined as the interval from the first documentation of objective response (RECIST v1.1) to the earlier of the first documentation of disease progression (per RECIST v1.1) or death from any cause. Any patients with an ongoing response will be censored on the date of the last post-baseline scan.

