## **Protocol Amendments**

This statistical analysis plan (SAP) incorporates the amendments in Table 2.

**Table 2** Protocol Amendments

Amendment	Date of Issue	Summary of Major Changes	
Amendment 1	05 July 2018	
 
Inclusion of patients who have achieved a partial response (PR) to their first platinum-based regimen has been justified.
 
Language was added as requested by the MHRA to align safety assessments to the SmPC for nivolumab.
 
	
Amendment 2	26 October 2020	
 
The original comparison of rucaparib + nivolumab vs placebo was moved from the primary endpoint analysis to an exploratory endpoint analysis
 
Clarification that alpha will be split between the remaining 2 independent comparisons of ATHENA-COMBO (rucaparib + nivolumab vs rucaparib) and ATHENA-MONO (rucaparib vs placebo) treatment and that they will mature at different timepoints and be read out separately;
 
Update to the step-down analysis for the monotherapy comparison (rucaparib vs placebo), from tBRCA → HRD → ITT to HRD → ITT, due to a low proportion of tBRCA patients enrolled to the study.
 
	
Amendment 3	08 September 2021	
 
The step-down for ATHENA-COMBO was changed from an HRD → ITT analysis to an ITT analysis only. No changes to sample size and power assumptions were made.
 
Added an exploratory analysis for tBRCA, HRD, and PD-L1 subgroups of the combination comparison.
 
	
Amendment 4	29 November 2021	
 
The following changes were made per US FDA request:
 
Removed bicrPFS from the hierarchical step-down and added bicrPFS as a stand-alone secondary endpoint.
 
Added language clarifying the key secondary endpoints in the step-down analysis are OS and ORR and that secondary endpoints of bicrPFS and DOR were outside of the step-down procedure.
 
Included further details on PFS censoring methodology
 
	

Confidential 15 of 52

Amendment 5	16 June 2023	Clovis Oncology has transferred Sponsor responsibilities to pharma&; added language to update pharma& contacts.
		
 
Updated the current rucaparib approvals in the US, EU, and UK.
 

		• Discontinued the requirement for ctDNA collection in the long-term follow-up portion of the study.
		
 
Updated the use of log-rank test for official test for step-down procedure (per FDA request).
 

		
 
Added information on ARIEL4 study.
 

		Updated the safety overview.

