### 10 EFFICACY ANALYSIS

## 10.1 Primary Efficacy Analysis

The primary efficacy endpoint is PFS as assessed by the investigator (invPFS). The time to invPFS will be calculated in months as the time from randomization to disease progression +1 day, as determined by RECIST v1.1 criteria or death due to any cause, whichever occurs first. Only scans or deaths prior to and on the start of any subsequent anticancer treatment will be used in PFS analysis. Any deaths or progression events occurring within 2 missing expected scan assessments will be included in the analysis. Two missed scans or visits is defined as a duration of 26 weeks (12 x 2+2) for the first 3 years and 50 weeks (24 x 2+2) thereafter. Events occurring immediately after 2 consecutive missed scans will be censored as below.

Censoring rule: Any patients who do not experience an event of either disease progression or death will be censored on the last on-study tumor assessment prior to start of any subsequent anticancer treatment. Any patient with an event of either disease progression or death following 2 or more missed expected consecutive scans will be censored on the date of the last on-study tumor assessment prior to the gap in scan collection. If a patient has an evaluable non-PD scan immediately following the gap, the gap-clock will reset and subsequent scans and events (progression or death) may be used in the primary PFS assessment (barring intervening SACT, as above). If a patient does not have any on-study tumor assessments, then the patient will be censored on the date of randomization (ie, Day 1).

The overall tumor assessment date for visits where multiple scans were utilized to make the assessment will be based on the following rule: the scan date showing the disease progression will be used for events where there is disease progression. For censored patients, the later date of the tumor scans within the assessment will be used.

The randomization stratification factors included in the primary analysis of invPFS are:

- HRD classification (tBRCA, non-tBRCA LOHhigh, non-tBRCA LOHlow, or non-tBRCA LOHunknown) by central laboratory analysis;
- Disease status post-chemotherapy (residual disease vs no residual disease); and
- Timing of surgery (primary surgery vs interval debulking).

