## 10.3.3 Progression Free Survival 2 (PFS2)

The second event of progression, PFS2, is defined as the time from randomization to the second event of disease progression as assessed by the investigator, or death due to any cause. The second event will be the disease progression event as reported during the subsequent anticancer follow up. Subsequent anticancer treatments will be collected for all patients every 12 or 24 weeks (± 14 days), until death, loss to follow-up, withdrawal of consent from study, or closure of the study. The subsequent anticancer data with start and stop date and any date of progression will be documented. The date of progression on subsequent anticancer treatments may be a documented event per RECIST guidelines or may be an event of symptomatic/clinical or CA-125 progression. Patients who have not died or had a second event of disease progression will be censored on the date the patient was last known to be alive or last visit. PFS2 will be analyzed using Cox proportional hazard methodology and a stratified log-rank test. The stratified hazard ratio (and 95% confidence interval) from the Cox proportional hazards model will be used to estimate the HR between the randomized treatment groups.

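### The COMBO SAP ends duration of response at documented progression and has no rule for a responder who dies without it, while the protocol counts death as an event

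*SAP*

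**What the plan says.** COMBO SAP 10.2.4 analyses DOR in patients with a confirmed RECIST response. Its definition sentence says that the duration "will be measured from the date of the first response until the first date that progressive disease is documented". A second sentence gives the calculation, from the first scan showing response to the first scan showing progression, plus one day. There is one censoring rule: "Any patients with an ongoing response will be censored at the date of the last post-baseline scan". The section does not mention death, and no other section of that SAP supplies a death rule for DOR.

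Protocol 9.6.2.4 runs DOR from the first documented response "to the earlier of the first documentation of disease progression (per RECIST v1.1) or death from any cause". The synopsis, under Secondary Efficacy Endpoints, defines it the same way.

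For its other progression endpoints the COMBO SAP does name death:
- invPFS in 10.1: "as determined by RECIST v1.1 criteria or death due to any cause, whichever occurs first"
- bicrPFS in 10.2.1: "according to RECIST v1.1 criteria as assessed by BICR, or death due to any cause, whichever occurs first"
- PFS2 in 10.3.3: "the time from randomization to the second event of disease progression as assessed by the investigator, or death due to any cause"

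The only DOR entry in its table of protocol amendments (Table 2, Amendment 4) is that the "secondary endpoints of bicrPFS and DOR were outside of the step-down procedure". Its Introduction presents the SAP as adding detail to analyses the protocol already outlines.

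Two other places leave death out. Protocol Appendix 1, the general RECIST summary, ends the duration of overall response when recurrence or progression is objectively documented. MONO SAP 10.2.4 has the same calculation and censoring sentences as COMBO, though without a separate definition sentence. It adds that only scans used for the primary endpoint count towards DOR.

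**The concern.** A confirmed responder in Arm A or Arm B who dies before progression is documented is an event under the protocol. Under COMBO SAP 10.2.4 that patient has no progression scan to end the interval, and calling the response ongoing is a strained description of someone who has died. Whoever programs the endpoint must choose. If the choice is to censor, the reported quantity is time to progression among responders, not the protocol's DOR.

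DOR is a named secondary endpoint with a planned Cox model, log-rank test and median. The same method carries over to the exploratory summaries by PD-L1 status (10.3.1), Arm C against Arm D (10.3.4) and Arm A against Arm D (10.3.5). Censoring deaths lengthens the median relative to the protocol definition, and it shifts the hazard ratio if the share of deaths differs between arms.

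**Working it through.** The documents give no sample size, event count or power for DOR, so there is no plan figure to reproduce. The check is textual, followed by an illustration of size.

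**1. The definitions side by side.**

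| Source | What ends DOR | Responder who dies without progression |
|---|---|---|
| Protocol synopsis and 9.6.2.4 | Progression or death, whichever is earlier | Event at death |
| Protocol Appendix 1 | Documented recurrence or progression | Not addressed |
| COMBO SAP 10.2.4 | Documented progression (definition and calculation) | Not addressed |
| MONO SAP 10.2.4 | First progression scan (calculation only) | Not addressed |

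**2. Is a change declared?** No. Neither Table 2 nor the Introduction of the COMBO SAP announces a new definition of DOR.

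**3. Is the wording only shorthand?** The calculation sentence proves little. In COMBO SAP 10.2.1 the bicrPFS calculation also runs to progression only, although its definition includes death. The definition sentence is the real evidence: invPFS, bicrPFS and PFS2 each have death in theirs, and DOR does not.

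**4. Size if deaths are censored.** Let s be the share of first events in responders that are deaths without documented progression. The documents do not give it, so 5% to 20% is assumed. With constant hazards λP for progression and λD for death, s = λD/(λP + λD). The composite median is ln 2/(λP + λD), and the median with deaths censored is ln 2/λP. The ratio is 1/(1 − s):
- s = 5%: 1/0.95 = 1.05
- s = 10%: 1/0.90 = 1.11
- s = 20%: 1/0.80 = 1.25

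This censors at the death date and ignores the scan grid. Censoring at the last scan, as the SAP rule would do, makes it approximate.

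**5. How many patients.** The earlier rucaparib maintenance study had 26 confirmed responders (Protocol 1.1.1.2.2.2) among 375 rucaparib patients (Protocol Table 1). For 400 patients, 26/375 × 400 = 27.7, about 28. That study was in recurrent disease, so the figure is indicative only. Multiplying 27.7 by s gives 1.4, 2.8 and 5.5 responder deaths per arm. These are upper bounds for each s, because they suppose that every responder has had a first event.

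With so few patients the median ratio varies by chance. In 20,000 simulated arms of 28 responders (exponential DOR, composite median 12 months, deaths censored at death), the 10th to 90th percentiles of the ratio were 1.00–1.27, 1.00–1.43 and 1.04–1.74 at s = 5%, 10% and 20%.

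**6. Effect on the hazard ratio.** Censoring deaths multiplies the A/B hazard ratio by (1 − sA)/(1 − sB):
- sA = 10%, sB = 5%: 0.90/0.95 = 0.95; reversed, 1.06
- sA = 20%, sB = 10%: 0.80/0.90 = 0.89; reversed, 1.13

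For scale, with 28 events per arm the 95% confidence limits lie a factor of exp(1.96 × √(2/28)) = 1.69 either side of the estimate.

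**The case against.** The strongest reply is that this is a drafting slip with a plain answer. The COMBO SAP says it elaborates on the protocol and declares no change to DOR, so the protocol definition should govern. The SAP sentence closely resembles the RECIST summary in protocol Appendix 1, which also omits death, so the protocol itself carries both wordings. MONO SAP 10.2.4 has the same calculation and censoring sentences. The assumed death share has no support in the documents, and the hazard-ratio shift is small beside the imprecision of a comparison with about 28 events per arm.

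Most of this stands. A reader might infer that the sponsor deliberately redefined DOR for COMBO, or that the defect belongs to COMBO alone. The documents support neither: inadvertent omission is the natural reading, and MONO shares the gap.

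What the reply does not do is make the texts agree. Appendix 1 is a general summary of response criteria, whereas 9.6.2.4 and the synopsis are the trial's own endpoint definitions and both name death. Programming follows the SAP, and reading its ongoing-response rule as covering patients who have died would contradict the protocol.

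**Conclusion.** COMBO SAP 10.2.4 does not match the protocol's DOR and leaves responder deaths without a rule. It should be corrected.

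If deaths are censored, the median is overstated by a factor of about 1.05 to 1.25. That range rests on an assumed death share of 5% to 20%, constant hazards and no scan grid. The hazard ratio could move either way, by an amount that is small against its confidence interval.

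A reader might infer a threat to type I error or to the main conclusions. There is none: DOR is a stand-alone secondary endpoint outside the step-down (COMBO SAP 9.3), analysed in a small subset, and no alpha, step-down test or primary result depends on it.

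A reader might also treat the chemotherapy-free interval and the times to first and second subsequent treatment as the same error. COMBO SAP 10.3.9 counts only the start of therapy, while MONO SAP 10.3.7 also counts death. The protocol does not define these endpoints, and COMBO analyses them as exploratory without multiplicity adjustment (10.3). Harmonising them is optional, and the difference is not a departure from the protocol.

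**What to change.** In COMBO SAP 10.2.4:
- Define DOR as the time from first response to the earlier of first documented progression or death from any cause, as in protocol 9.6.2.4.
- Censor at the last post-baseline scan only responders who are alive without progression.
- State that scans and deaths after subsequent anticancer therapy, or after two missed scans, follow the invPFS rules in 10.1, or state and justify another rule. Protocol 9.6.2.4 is silent on these cases. Without a rule, a responder who starts new therapy and later dies without documented progression would be censored for invPFS but counted as a DOR event.

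Check how responder deaths were handled for MONO DOR and report Arm B consistently in both comparisons. Otherwise, correcting COMBO alone could give the shared arm two definitions of DOR.

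Make the change before the COMBO blind break. If that has passed, report DOR by the protocol definition and disclose the change.

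The cost is a few sentences in the SAP, a small change to the DOR derivation and the MONO check. Deaths are already collected for overall survival, so no new data and no protocol amendment are needed. Reported medians may be slightly shorter.
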